8.3.5. Reporting Serious Adverse Events (SAEs)

The investigator is responsible for ensuring that all SAEs observed by the investigator or reported by the subject that occur after signing of the informed consent/assent through 28 days after the last dose of pamrevlumab are recorded in the subject's medical record and are submitted to FibroGen. All SAEs must be submitted to FibroGen within 24 hours following the investigator's knowledge of the event via the SAE report form. Additionally, pamrevlumab related SAEs (including deaths) that occur after the EOS/safety follow-up visit will be reported.

If a subject is permanently withdrawn from protocol required therapies because of a serious adverse event, this information must be submitted to FibroGen. FibroGen will report serious adverse events and/or suspected unexpected serious adverse reactions as required to regulatory authorities, investigators/institutions, and central IRBs/IECs in compliance with all reporting requirements according to local regulations and Good Clinical Practice (GCP).

To report an SAE, the investigator must complete an SAE Report Form and fax or email the completed form to the Sponsor or its designated safety management vendor.

Full details of the SAE should also be recorded on the medical records and in the CRF. The following minimum information is required:

- Subject number, sex and age
- The date of report
- A description of the SAE (event, seriousness of the event)
- Causal relationship to the study drug

Follow-up information for the event should be sent promptly.

For each SAE observed, the investigator should obtain all of the information available about the event, including (but not limited to): hospital discharge diagnoses, hospital discharge note, death certificate, appropriate laboratory findings (including autopsies and biopsy results), and clinical examinations (including radiological examinations and clinical consultations).

8.3.5.1. Reporting Serious Adverse Events to the Institutional Review Board / Independent Ethics Committee

The investigator is responsible for notifying his/her Institutional Review Board (IRB) or Ethics Committee (EC) of SAEs in accordance with local regulations and IRB/EC requirements. The Sponsor, or its designated safety vendor, will provide a copy of expedited safety reports to the investigator that it intends to submit to global regulatory authorities.

8.3.5.2. **Deaths**

The investigator will report the fatal event to the Sponsor's medical monitor. The investigator must provide a causal assessment of the relationship of the event to the study drug according to the guidance in Section 8.3.4.

If the death occurred within the AE collection and reporting period (signed ICF to 28 days after last dose) and meets the reporting criteria, the investigator must submit the SAE Report Form in the same manner as described above in Section 8.3.5. If the investigator becomes aware of a

Confidential

death occurring after the AE reporting period and considers it related to pamrevlumab, it will be reported as an SAE.

8.3.6. Pregnancies: Reporting and Follow-up of Subjects and Female Partners of Subjects

The outcome of all pregnancies for female subjects or female partners of male subjects should be followed up and documented as described. If a female subject or a female partner of a male subject becomes pregnant while the subject is receiving study treatment or within 12 weeks after the last dose of study treatment, a Pregnancy Report Form must be completed and submitted to the Sponsor or designated safety management vendor within 24 hours of the investigator becoming aware of the pregnancy. The investigator must follow-up to completion of the pregnancy to ascertain its outcome (e.g., spontaneous miscarriage, elective termination, ectopic pregnancy, normal birth or congenital abnormality) and whether any AEs occur during the pregnancy or birth. The outcome of the pregnancy must be reported by the investigator on a Pregnancy Outcome Report Form, which should be sent to the Sponsor and/or its designated safety vendor within 24 hours of the investigator becoming aware of the outcome.

Pregnancy itself is not an AE unless there is a suspicion that the investigational product under study may have interfered with the effectiveness of a contraceptive medication. Pregnancies are followed up to outcome even if the subject was discontinued from the study. Congenital abnormalities/birth defects and spontaneous miscarriages should be reported and handled as SAEs. Elective abortions without complications should not be handled as AEs.

If a lactation case occurs while the female subject is taking protocol-required therapies, or within 28 days after the last dose of study treatment, report the lactation case to FibroGen. In addition to reporting a lactation case during the study, investigators should monitor for lactation cases that occur after the last dose of protocol-required therapies through 3 months after the last dose of pamrevlumab. Any lactation case should be reported to FibroGen's Safety within 24 hours of the investigator's knowledge of event.

8.3.7. Laboratory or other Test Abnormalities/ Findings

All new or worsened laboratory abnormalities should be reported as AEs. If the abnormal laboratory finding is accompanied by signs or symptoms, report the signs and symptoms as the AE in lieu of the abnormal laboratory value. If a diagnosis is available, report the diagnosis.

8.3.8. Hypersensitivity/Anaphylactic Reactions:

Hypersensitivity and anaphylactic reactions will be monitored throughout the study, using the criteria below as defined per Sampson et al. 2006 (Sampson, 2006).

Anaphylaxis is highly likely when the following criteria is fulfilled:

1. Acute onset of an illness (minutes to several hours) with involvement of the skin, mucosal tissue, or both (e.g., generalized hives, pruritus or flushing, swollen lips-tongue-uvula).

And at least one of the following criteria:

- Respiratory compromise (e.g., dyspnea, wheeze-bronchospasm, stridor, reduced PEF, hypoxemia)
- b. Reduced BP or associated symptoms of end-organ dysfunction (e.g., hypotonia [collapse], syncope, incontinence)
- 2. Two or more of the following that occur rapidly after exposure to a likely allergen for that patient (minutes to several hours):
 - a. Involvement of the skin-mucosal tissue (e.g., generalized hives, itch-flush, swollen lips-tongue-uvula)
 - b. Respiratory compromise (e.g., dyspnea, wheeze-bronchospasm, stridor, reduced PEF, hypoxemia)
 - c. Reduced BP or associated symptoms (e.g., hypotonia [collapse], syncope, incontinence)
 - d. Persistent gastrointestinal symptoms (e.g., crampy abdominal pain, vomiting)
- 3. Reduced BP after exposure to known allergen for that patient (minutes to several hours):
 - a. Systolic BP of less than 90 mm Hg or greater than 30% decrease from that person's baseline

8.3.9. Safety Monitoring

Safety will be assessed throughout the study. A medically complete baseline profile of each subject will be established through medical history, a complete physical examination including vital signs, laboratory tests and PFTs. Any medically significant changes from baseline will be monitored throughout the study and appropriate interventions will be taken accordingly. Safety and tolerability will be monitored closely by FibroGen.

8.3.9.1. Special Reporting Situations

Special Reporting Situations on FibroGen investigational product Pamrevlumab that require safety evaluation include:

- Overdose (any dose greater than 4.1g)
- Suspected abuse/misuse
- Inadvertent or accidental exposure
- Medication error (e.g. incorrect dose administered)
- Drug-drug interactions

Report special situations to FibroGen's Safety within 24 hours of the investigator's knowledge of the event. See Study Reference Manual for detailed reporting instructions.

8.3.9.2. Data Monitoring Committee (DMC)

An Independent Data Monitoring Committee (DMC) will be utilized and will be composed of external experts. Composition and responsibilities of the DMC will be defined in a separate DMC charter. The DMC responsibilities will include an interim analysis for safety, in accordance with the DMC Charter and an Interim Analysis Plan.

9. STATISTICS

9.1. Sample Size Determination

The sample size of 65 subjects in each treatment arm will provide about 80% power, at 10% two-sided significance level, to detect a 20% difference in the proportion of subjects who never received mechanical ventilation / ECMO and alive at Day 28. This assumes that 65% of subjects in the placebo arm who never received mechanical ventilation and/or ECMO at Day 28, compared to 85% in the pamrevlumab group.

9.2. Analysis Populations

Enrollment and disposition summaries will be provided on all randomized subjects.

The Safety Population consists of all subjects who have received at least one dose of study drug. All safety summaries will be based on the Safety Population.

The Intent-To-Treat Set (ITT) consists of all randomized subjects. All efficacy analyses will be performed based on the ITT set.

9.3. General Considerations

Baseline value is defined as mean of all screening and Day 1 values prior to the first dose.

Descriptive summaries will be presented for study parameters including baseline characteristics, safety, and efficacy.

Continuous variables will be reported in mean, standard deviation or standard error, median, Q1-Q3, minimum, and maximum.

Categorical variables will be reported in frequency and percentage of subjects within each outcome category.

9.4. Statistical Methods

The analysis of the proportion of subjects who never received mechanical ventilation and/or ECMO and are alive at Days 14 and 28, the proportion of subjects alive, discharged home, and not on supplemental oxygen at Day 28, proportion of subjects' clinical status based on an 8-point ordinal scale, and proportion of subjects with categorical PaO₂/FiO₂ ratio endpoints will be conducted using logistic regression model with treatment group and adjusting for relevant baseline prognostic covariates.

The number of days in ICU/CCU (either on or off mechanical ventilation and/or ECMO) at Day 28, number of days on mechanical ventilation and/or ECMO at Day 28 will be analyzed using the analysis of covariance (ANCOVA).

Change in PaO₂/FiO₂ ratio to day 28, change in resting SpO₂ adjusted by FiO₂ to day 28, change in (non-invasive) oxygen supplementation requirements to day 28 will be analyzed using Mixed Model for Repeated Measures (MMRM) approach using relevant prognostic factors as covariates and treatment and Time and treatment *time interaction

The analysis will take into account the inter-current events as follows.

1. Treatment discontinuation (e.g., due to AEs, Withdrawal by Subject or Physician Decision): Missing endpoint will be imputed by the last result prior to discontinuation.

- 2. Death: Composite strategy: inter-current event is taken to be a component of the variable. For number of days not requiring mechanical ventilation at Day 14, number of days in ICU/CCU (either on or off mechanical ventilation and/or ECMO) at Day 28, and number of days on mechanical ventilation and/or ECMO at Day 28; days with missing data after death will be imputed with the worst result until Day 28.
- 3. Treatment discontinuation due to recovering and discharged from hospital: Missing endpoint will be imputed with the last result prior to discontinuation.

Treatment comparison analysis of time to event endpoints, will be performed using cox regression model adjusting for relevant baseline prognostic factors. Hazard ratios together with 95% two-sided confidence intervals for the hazard ratio will be provided.

Time to recovery by Day 28, time to mechanical ventilation/ECMO or all-cause mortality by Day 28, and all-cause mortality at Day 28 (proportion of subjects deceased), and time to death from any cause at Day 28 will be analyzed using Cox regression adjusting for relevant prognostics factors. Other methods will be used as appropriate.

9.5. Safety Analyses

All subjects who received any dose of pamrevlumab will be included in the safety analyses which will summarize treatment-emergent adverse events (TEAEs); treatment-emergent serious adverse events (TESAEs); clinical laboratory parameters and vital signs, as well as hypersensitivity/anaphylactic reactions.

10. ETHICS

10.1. Ethical Considerations

The study will be conducted in accordance with applicable regulatory requirements, the International Conference on Harmonisation (ICH) E6 Guideline for Good Clinical Practice (GCP) and Institutional Review Board (IRB) or Independent Ethics Committee (IEC) requirements.

This protocol, the Informed Consent Form, and the Investigator's Brochure must be approved by a properly constituted IRB/IEC before the study is initiated and before any investigational product is shipped to the investigator.

Investigators must maintain a list of appropriate qualified persons to whom the investigator has delegated significant trial-related duties and update the list as staff and their delegated responsibilities change.

Prior to participation in any study-specific procedures, the subject (or legally authorized representative) must sign an IRB/IEC-approved written Informed Consent Form (ICF) in his/her native language.

10.2. Communication with the Institutional Review Board or Independent Ethics Committee

This protocol, the Informed Consent Form, the Investigator's Brochure, and any information to be given to the subject must be submitted to a properly constituted IRB/IEC by the investigator for review and approved by the IRB/IEC before the study is initiated and before any investigational product is shipped to the investigator. In addition, any subject recruitment materials must be approved by the IRB/IEC before the material is used for subject recruitment.

The investigator is responsible for obtaining re-approval by the IRB/IEC annually or as required by the policies and procedures established by the IRB/IEC. Copies of the investigator's annual report and other required reports submitted to the IRB/IEC and copies of the IRB/IEC continuance of approval must be furnished to FibroGen or designee. A copy of the signed FDA Form 1572 or other qualified investigator statement (as required) must also accompany the above approval letter provided to FibroGen.

Investigators are also responsible for promptly informing the IRB/IEC of any protocol changes or amendments, changes to the Investigator's Brochure, and other safety-related communications from FibroGen or its designee. Written documentation of IRB/IEC approval must be received before the amendment is implemented.

Investigators must maintain a list of appropriate qualified persons to whom the investigator has delegated significant trial-related duties and update the list as staff and their delegated responsibilities change.

10.3. Subject Information and Consent

Prior to participation in any study-specific procedures, the subject must sign (note: all references to "subject" in this section refers to the study subject or his/her legally acceptable representative) an IRB/IEC-approved written Informed Consent Form (ICF) in his/her native language. The approved written informed consent must adhere to all applicable laws in regards to the safety and confidentiality of the subjects. To obtain and document informed consent, the Investigator should comply with applicable regulations, and adhere to ICH GCP standards.

The language in the written information about the study should be as non-technical as practical and should be understandable to the subject. Before informed consent is obtained, the Investigator should provide the subject ample time and opportunity to inquire about the study and to decide whether or not to participate.

All questions about the study should be answered to the satisfaction of the subject. The written ICF should be signed and personally dated by the subject and the person who conducted the informed consent discussion, with any additional signatures obtained as required by applicable local regulations and IRB/IEC requirements. Each subject will be informed that participation is voluntary and that he/she can withdraw from the study at any time. All subjects will receive a copy of the signed and dated ICF.

If there are any changes to the IRB/IEC approved ICF during the subjects' participation in the study, the revised ICF must receive the IRB/IEC's written approval before use and subjects must be re-consented to the revised version of the ICF, if/as required by the IRB/IEC.

Each subject (or legally authorized representative) must provide his or her consent for the use and disclosure of personal health information in accordance with applicable regulatory requirements.

10.4. Confidentiality

The confidentiality of records that could identify subjects should be protected, respecting the privacy and confidentiality rules in accordance with applicable regulatory requirements.

Subject medical information obtained as part of this study is confidential and may only be disclosed to third parties as permitted by the Informed Consent or other disclosure authorization documents signed by the subject, unless permitted or required by applicable law.

11. DATA HANDLING AND RECORD KEEPING

11.1. Source Documents

Source documents are original documents, data, and records necessary for the reconstruction and evaluation of the clinical study. The investigator or designee will prepare and maintain adequate and accurate source documents. These documents are designed to record all observations and other pertinent data for each subject enrolled in this clinical study. Source documents must be adequate to reconstruct all data transcribed onto the Case Report Forms (CRFs) and resolved queries.

11.2. Direct Access to Source Documents

The investigator must provide direct access to source data and source documents for trial-related monitoring, audits, IRB/IEC review, and regulatory authority inspection. Direct access includes examining, analyzing, verifying, and reproducing any records and reports that are important to the evaluation of the study. The investigator is obligated to inform and obtain the consent of the subject to permit such individuals to have access to his/her study-related records, including personal information and medical records.

11.3. Data Collection, Handling, and Verification

All required data will either be entered onto CRFs by authorized site personnel or will be provided as a data transfer from authorized service providers (such as laboratory results). Data will be entered or uploaded into a validated, clinical database compliant with 21 CFR Part 11 regulations.

All subject data will be reviewed by Sponsor and/or designee. Data that appear inconsistent, incomplete or inaccurate will be queried for site clarification.

Adverse events and medications will be coded using industry standard dictionaries (e.g., MedDRA and World Health Organization Drug [WHODrug]) Dictionary.

The investigator is responsible for reviewing, verifying, and approving all subject data (i.e. CRFs and queries) throughout the duration of the study and prior to study completion, ensuring that all data are verifiable with source documents.

11.4. Protocol Deviations

Unless there is a safety concern, there should be no deviations or violations of the study protocol. In the event of a safety concern, the Investigator or designee must document and explain the reason for any deviation from the approved protocol. The Investigator may implement a deviation from, or a change to, the protocol to eliminate an immediate hazard to study participants without prior IRB/IEC approval. Immediately after the implemented deviation or change, the Investigator must submit a report explaining the reasons for the protocol violation or deviation to the IRB/IEC, FibroGen, and to the regulatory authorities, if required.

11.5. Retention of Data

A FibroGen representative will inform the Investigator in writing when it is acceptable to dispose of any study records. To enable evaluation and/or audits from regulatory authorities or FibroGen or designee, the Investigator agrees to keep records, including the identity of all participating subjects (eg, subject identification code list and all source documents), all original signed ICFs, copies of all CRFs, original laboratory reports, detailed records of drug disposition and all essential documents for the conduct of a clinical study. To comply with international regulations, the records should be retained by the Investigator for at least 2 years after the last approval of a marketing application in an ICH region and until there are no pending or contemplated marketing applications in an ICH region, or until at least 2 years have elapsed since the formal discontinuation of clinical development of the investigational product. However, the Investigator may need to retain these documents for a longer period if required by applicable law, regulatory requirements or by an agreement with FibroGen whichever is longer.

11.6. Financial Disclosure

The Investigator's disclosable financial interests must be obtained prior to initiation of the study site, at completion of the study at the investigational site, and 1 year following study completion.

The Investigator should promptly update this information if any relevant changes occur during the above described period.

Disclosable financial interests will be recorded on the Investigator Financial Disclosure Form.

Any Investigator(s) added as investigational staff to the form FDA 1572 or other qualified investigator statement must complete the Investigator Financial Disclosure Form at the beginning of his/her participation in the study. The Investigator Financial Disclosure Form for any Investigator(s) leaving the clinical site prior to study completion will be obtained prior to study completion.

12. PUBLICATION POLICY

The data and results of the study will be owned solely by FibroGen and shall be confidential information of FibroGen, subject to the Investigator's publication rights, described below and if any outlined in the Clinical Trial Agreement. It is understood by the Investigator that FibroGen may use the information developed in this clinical study in connection with the development of its compounds and therefore, may disclose it as required to other clinical investigators, the

Licensing Authority or to regulatory agencies of other governments. To allow for the use of the information derived from this clinical study, the Investigator understands that he/she has an obligation to provide and disclose test results and all data developed during this study to FibroGen.

Any publication or presentation of the results of this clinical study by the Investigator may only be made in strict compliance with the provisions of the Clinical Trial Agreement. Any publication relating to the study shall be made in collaboration with FibroGen. The Investigator should understand that it is not FibroGen's intention to prevent publication of the data generated in the clinical study. However, FibroGen reserves the right to control the form and timing of such publication for commercial reasons. The Study Center and Investigator shall adhere to the publication language as outlined in both Clinical Trial Agreement and the protocol to the extent that if there is any conflict or ambiguity between Clinical Trial Agreement and the protocol, the publication terms in the Clinical Trial Agreement shall prevail.

³ Need for mechanical ventilation/ECMO, including ventilator settings, or supplemental oxygen, including mode of oxygen delivery. ⁴ Collected until Day 28 or hospital discharge, whichever occurs earlier 5 ABGs are collected daily while in ICU/CCU, and recorded if performed as part of routine care outside of ICU/CCU, until Day 28 or hospital discharge, whichever occurs earlier ⁶ if subject is discharged, these visit do not apply; subject should return for infusion visits only. ⁷ If a subject is discharged from hospital before Day 28, and unwilling to return for visits and infusions in an outpatient setting, visits may be conducted remotely for assessment of vital status and safety. If a subject is lost to follow-up after hospital discharge, vital status may also be obtained from public records. 8 Visit windows, for outpatient dosing visits ONLY: visit window for Day 14: +/- 2 days. Visit window for Day 28: +/- 3 days.

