3.2. Efficacy Assessments

Primary Efficacy Endpoint

Proportion of subjects who never received mechanical ventilation and/or ECMO and alive at Day 28

Secondary Efficacy Endpoints

- Proportion of subjects alive, discharged home, and not on supplemental oxygen at Day 28
- Proportion of subjects who never received mechanical ventilation and/ or ECMO and alive at Day 14
- Time to recovery by Day 28 based on 8-point ordinal scale (Day of recovery is defined as the first day on which the patient satisfies one of the following three categories from the ordinal scale: 1) Hospitalized, not requiring supplemental oxygen; 2) Not hospitalized (discharged), but with limitation on activities and/or requiring

home supplemental oxygen; 3) Not hospitalized (discharged), with no limitations on activities and not requiring supplemental oxygen

- Clinical status based on 8-point ordinal scale (time range: Days 1 to 28)
- Days in ICU/CCU (either on or off mechanical ventilation and/or ECMO) at Day 28
- Days on mechanical ventilation and/or ECMO at Day 28
- Time to mechanical ventilation/ECMO or all-cause mortality at Day 28
- All-cause mortality at Day 28 (proportion of subjects deceased)
- Time to death from any cause at Day 28
- Change in PaO₂/FiO₂ ratio as categorical variable using Berlin criteria for ARDS categorization (mild, moderate, severe) (time range: Days 1 to 28)
- Change in PaO₂/FiO₂ ratio as continuous variable (time range: Days 1 to 28)
- Change in resting SpO₂ adjusted by FiO₂ (time range: Days 1 to 28)
- Change in (non-invasive) oxygen supplementation requirements (time range: Days 1 to 28)

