6.2. Modified WHO Ordinal Scale

Assessment of clinical status, using an 8-Point, Modified WHO Ordinal Scale as specified below, should be assessed daily, until Day 28:

- 1. Not hospitalized, no limitations on activities
- 2. Not hospitalized, limitations on activities and/or requiring home oxygen
- 3. Hospitalized, not requiring supplemental oxygen, no longer requiring medical care
- 4. Hospitalized, not requiring supplemental oxygen, requiring ongoing medical care (COVID-19-re; ated or otherwise)
- 5. Hospitalized, requiring supplemental oxygen
- 6. Hospitalized, requiring nasal high-flow oxygen, non-invasive mechanical ventilation, or both
- 7. Hospitalized, requiring invasive mechanical ventilation, extra-corporeal membrane oxygenation (ECMO), or both
- 8. Death

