6.3. Concomitant Medications, Supplemental Oxygen Needs, and other Care

Subjects will be treated according to best available standard-of-care according to the judgment of the Investigator. All concomitant medications, including approved and non-approved treatments for COVID-19 (e.g., hydroxychloroquine, IL-6 inhibitors, etc.), as well as supplemental oxygen needs, will be collected and recorded.

In addition, the following will be recorded and collected: documentation of SARS-Cov-2 infection, documentation of any other infection(s) prior to or during hospitalization, and whether or not aggressive care is withheld or withdrawn, including the reason for withholding or withdrawal of care (e.g., DNR/DNI order, resource limitation). Vital status may also be obtained from public records.

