Proportion of subjects by response category on the NIAID 8-point ordinal scale will be summarized descriptively based on observed data at baseline and Day 28.

Order	Ordinal Level
1	Not hospitalized, no limitations on activities
2	Not hospitalized, limitations on activities and/or requiring home oxygen
3	Hospitalized, not requiring supplemental oxygen, no longer requiring medical care (used if hospitalization was extended for infection-control reasons)
4	Hospitalized, not requiring supplemental oxygen, requiring ongoing medical care (COVID-19-related or otherwise)
5	Hospitalized, requiring supplemental oxygen
6	Hospitalized, requiring high-flow oxygen, non-invasive mechanical ventilation, or both

7	Hospitalized, requiring invasive mechanical ventilation, extra-corporeal membrane oxygenation (ECMO), or both
8	Death
Missing	

9.5 Number of Days in ICU/CCU and Number of Days on Mechanical Ventilation and/or ECMO

Total number of days in ICU/CCU (either on or off mechanical ventilation and/or ECMO) at Day 28 and total number of days on mechanical ventilation and/or ECMO at Day 28 will be summarized descriptively.

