9.6 Change in Categorical PaO₂/FiO₂ Ratio (Mild, Moderate, and Severe)

PaO₂/FiO₂ ratio will be defined as a categorical variable using Berlin criteria for ARDS categorization (mild, moderate, severe), where mild is PaO₂/FiO₂ from >200 to <=300, moderate is from 100 to <=200, and severe is <100. Proportion of subjects of each category at baseline and Day 28 will be summarized descriptively.

9.7 Change from Baseline in PaO₂/FiO₂ Ratio and Change from baseline in Resting SpO₂/FiO₂ at Day 28

Change from baseline in PaO₂/FiO₂ ratio at Day 28 and change from baseline in resting SpO₂ adjusted by FiO₂ (SpO₂/FiO₂) at Day 28 will be summarized descriptively.

9.8 Change in (Non-invasive) Oxygen Supplementation Requirements at Day 28

The non-invasive oxygen supplementation requirements include:

- (1) No oxygen supplementation (including breathe room air or have been discharged from hospital)
- (2) Non-invasive oxygen supplementation -nasal cannula and face-mask

Change in non-invasive oxygen supplementation requirements will be presented by proportion of subjects with non-invasive oxygen supplementation requirements at baseline and at Day 28.

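### SAP 9.8 tabulates every discharged subject as needing no oxygen at Day 28, although the SAP's own ordinal scale and the first secondary endpoint allow for oxygen at home

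*Protocol*

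**What the plan says.** SAP 9.8 summarises the change in non-invasive oxygen requirements as proportions at baseline and at Day 28. It has two categories. The first is "No oxygen supplementation (including breathe room air or have been discharged from hospital"; the second is "Non-invasive oxygen supplementation -nasal cannula and face-mask". Nothing excepts a discharged subject who uses oxygen at home.

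Two other places treat discharge and oxygen use as separate facts:

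- SAP 9.4, ordinal level 2: "Not hospitalized, limitations on activities and/or requiring home oxygen".
- Protocol 3.2 (as amended), first secondary endpoint, repeated in SAP 4.2 and 9.2: "Proportion of subjects alive, discharged home, and not on supplemental oxygen at Day 28".

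In the protocol's Schedule of Assessments (Appendix 1), the row for oxygen supplementation needs carries footnote 4: "Collected until Day 28 or hospital discharge, whichever occurs earlier". SAP 9 says that efficacy is summarised on observed data and that missing endpoint values are not imputed.

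**The concern.** A subject at home on oxygen on Day 28 fails the first secondary endpoint, belongs at level 2 in SAP 9.4, and is placed in the no-oxygen category of SAP 9.8. The three tables would then describe the same person inconsistently, and the 9.8 entry would be the wrong one.

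The error has one direction. Eligibility requires hospitalization, so the discharge clause cannot act at baseline. It acts only at Day 28, and there it can only move subjects from oxygen to no oxygen. The reported fall in oxygen need can therefore be too large but never too small because of this rule.

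The clause also sits badly with SAP 9. For a subject discharged before Day 28 the dedicated oxygen item has no Day-28 value, and 9.8 supplies one from discharge status. That is an imputation in effect, though it is not called one.

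**Working it through.** The plan gives no figure on this point, so the check is a comparison of texts followed by an illustration of size.

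**Step 1: one subject through three definitions.** Take a subject discharged on Day 20 who is at home using oxygen on Day 28.

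| Place | Result for this subject |
|---|---|
| SAP 9.2, first secondary endpoint | Not a success: discharged, but on oxygen |
| SAP 9.4, ordinal scale | Level 2 |
| SAP 9.8 | No oxygen supplementation |

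If discharge implied no oxygen, the oxygen condition in the first secondary endpoint would be redundant and the home-oxygen wording of level 2 would be empty. The plan does not treat discharge that way outside 9.8.

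**Step 2: what the records can settle.** The ordinal scale "should be assessed daily, until Day 28" (Protocol 6.2), and its schedule row does not carry footnote 4. Level 1 settles the matter, because Protocol 3.2 words the matching recovery category as "Not hospitalized (discharged), with no limitations on activities and not requiring supplemental oxygen". Level 2 does not settle it alone, because it merges home oxygen with limited activity. The schedule row for concomitant medication and non-drug therapies continues to Day 28 and the follow-up visit. Protocol 6.3 says that concomitant medications, "as well as supplemental oxygen needs, will be collected and recorded", with no stop at discharge. These records may resolve level 2, but neither is named as a source in SAP 9.8.

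**Step 3: size.** Inputs: 22 subjects randomized (SAP 1) and 1:1 allocation (SAP 3). Assumptions: 22/2 = 11 per arm, all observed at Day 28. The actual split and the number on home oxygen are not in the documents.

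Shift in an arm's on-oxygen proportion per misplaced subject = 1/n:

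- n = 11: 1/11 = 9.1 points
- n = 9: 1/9 = 11.1 points
- n = 13: 1/13 = 7.7 points

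With one such subject in 11 and nobody else on oxygen, using the Clopper-Pearson 95% interval named in SAP 5.1:

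- Reported under 9.8: 0/11 = 0%, interval 0 to 28.5%
- If home oxygen was recorded and counted: 1/11 = 9.1%, interval 0.2 to 41.3%
- If no record exists: the subject is unknown, giving 0/10 observed with one unknown

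Two such subjects in 11 shift the proportion by 2/11 = 18.2 points.

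**The case against.** The strongest reply is that 9.8 is a separate endpoint that states its convention openly. The convention also fits a dedicated oxygen item that ends at discharge, and any reader can see what was counted. This stands in part: nothing is hidden. But 9.8 is titled as oxygen requirements at Day 28, it is not restricted to inpatients, and it explicitly classifies discharged subjects. The label then claims more than the rule supports.

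A second reply is that the information is visible elsewhere. SAP 9.4 tabulates level 2 and missing, SAP 5 puts all collected data in listings, and SAP 8.1 lists medications for the ITT population. With 22 subjects, any home-oxygen record that was collected could be found. This limits the harm, but it does not correct the 9.8 table, and the level-2 count does not say how many subjects are on oxygen.

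A third reply, that 0/11 instead of 1/11 presumes a record of home oxygen, is right. Without one, the honest figure is 0/10 with one unknown.

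Three stronger readings are tempting, and the documents do not support them:

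- A reader might infer from footnote 4 that no oxygen information exists after discharge. The footnote limits one item; the records in step 2 continue.
- A reader might infer that the SAP 9.2 endpoint cannot be derived. SAP 9.2 names no source for oxygen status at home, but that is missing detail. Continuing records may supply the status, a subject who cannot be classified is left out under the observed-data rule, and a source may be named in the case report form or table specifications, which are not available here.
- A reader might infer that the two 9.8 categories overlap for someone at home on a nasal cannula. Category 1 names discharge explicitly, so as written it governs, and the direction of the error is not in doubt.

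**Conclusion.** The discharge clause in SAP 9.8 is wrong as written. It conflicts with level 2 in SAP 9.4 and with the first secondary endpoint, and it can only understate oxygen need at Day 28.

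The consequence is minor. At an assumed 11 per arm, one subject with recorded home oxygen changes the arm's proportion by 9.1 points, but whether there was any such subject is unknown. The results are descriptive: SAP 5.1 rules out treatment comparisons, so no test is affected. The primary endpoint does not use this item.

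Confidence is high that the definitions conflict. The size is an illustration that rests on the assumed arm size, complete Day-28 observation and, for the 1/11 comparison, a record of home oxygen.

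**What to change.** In SAP 9.8, replace the discharge clause of category 1 with *or discharged and recorded as off oxygen*, and define that as ordinal level 1, or level 2 with therapy records showing no oxygen. Count a discharged subject with recorded home oxygen as on oxygen. Add a row, *discharged, oxygen status unknown*, for the remainder.

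The same derivation can serve the oxygen component of SAP 9.2, so that both tables treat a subject alike.

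The cost is one changed phrase and a short derivation in the SAP, one extra table row that may be empty, and a check of existing records for 22 subjects. No new data are needed. If the outputs are already final, a footnote to the 9.8 table saying that discharged subjects were counted as off oxygen by rule would at least keep the proportion from being misread.
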